3.11. Visit Windows

It is expected that all visits should occur according to the protocol schedule. All data will be tabulated per the evaluation visit as recorded on the CRF even if the assessment is outside of the visit window. In data listings, the relative day of all dates will be presented.

For analyses of IgG ELISA antibody titers and neutralizing antibody titers, analysis visits will be derived based on the relative study day (i.e., Rel Day, defined in Section 3.2) as outlined in the schedule of assessments with an expanded interval of +/-5 days. If there is more than one immunogenicity assessment during a given interval for analysis, the immunogenicity assessment within the protocol-specified interval (+/- 2 days) will be used. If there is still more than one immunogenicity assessment with the protocol-specified interval, the assessment closest to the target protocol-specified day will be used, i.e., if there is more than one immunogenicity assessment at the protocol-specified Day 29±2 days, the assessment closest to Day 29 will be used.

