2. SUBJECT POPULATION

2.1. Population Definitions

The following subject populations will be evaluated and used for presentation and analysis of the data:

- All Subjects as Treated (ASaT) Population: All subjects who received a partial or full dose of 1 single study injection, excluding subjects who have no on-study safety data. The subjects will be analyzed according to treatment received in case of a treatment error.
- Per-Protocol (PP) Population: All randomized subjects who received the vaccine dose to which they were randomized, have PHV01 IgG ELISA titer or PsVNA results on Days 1 (baseline) and 29 (± 5 days), and do not have any protocol violations that influence interpretation of immunogenicity endpoints.
- Modified Intent-to-Treat (mITT) Population: All randomized subjects who received a single study injection and have at least 1 post-injection immunogenicity evaluation. The subjects will be analyzed according to treatment received in case of a treatment error.

The ASaT population is the primary population for the analysis of safety endpoints. The PP population is the primary population for the analysis of immunogenicity parameters. The mITT population may be used for additional analyses of immunogenicity endpoints, should there be a 10% difference or more in the sizes of the mITT and PP analysis sets (see Section 4.3). Intervals for analysis, i.e., visit windows, are further defined in the Schedule of Events.

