3.10. Missing, Unused, and Spurious Data

In general, there will be no substitutions made to accommodate missing data points. All data recorded on the case report form will be included in data listings that will accompany the CSR.

Subjects with negative post-baseline antibody response (defined as the corresponding titers < LLOQ) will have a titer value assigned as LLOQ/2.

When tabulating AE data, partial dates will be handled as follows. If the day of the month is missing, the onset day will be set to the first day of the month unless it is the same month and year as study treatment. In this case, in order to conservatively report the event as treatment-emergent, the onset date will be assumed to be the date of treatment. If the onset day and month are both missing, the day and month will be assumed to be January 1, unless the event occurred in the same year as the study treatment. In this case, the event onset will be coded to the day of treatment in order to conservatively report the event as treatment-emergent. A missing onset date will be coded as the day of treatment.

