4.3. Immunogenicity Evaluation

Immunogenicity analyses will be conducted using the PP population. Supportive analyses of immunogenicity will be based on the mITT population if the number of subjects excluded from PP population is more than 10%.

4.3.1. Geometric Mean Titers and Mean Fold Increase of IgG ELISA Antibody and Neutralizing Antibody PsVNT

For IgG ELISA antibody titers and neutralizing antibody titers PsVNT (PsVNT₅₀ and PsVNT₈₀), GMT, and 95% confidence limit will be provided on Days 1, 8 (if tested), 15, 29, 85, and 181, where the GMT is calculated as the anti-log of the base-2 log transformed mean and the same for the corresponding confidence limit. Results will be presented by treatment group along with a combined PHV01 group, and the descriptive statistics will include the GMT, the geometric standard deviation, 25th percentile, median, 75th percentile, minimum, and maximum values. If appropriate, the analyses will be repeated for the GMT using the anti-log of the base-10 log transformed mean.

Pairwise comparison of the above antibody titer levels for each PHV01 dose level to one another and to the placebo group, as well as the comparison of the combined PHV01 dose group relative to the placebo group will be performed with Satterthwaite t-tests. T-tests will be performed on log-2 transformed values and the resulting estimated mean difference and associated 95% CI will then be back transformed using base-2 antilogarithms to obtain estimates

on the ratio scale. If appropriate, the analyses will be repeated using base-10 log transformed values and back transformed using base-10 antilogarithms to obtain estimates. In the event of extreme outliers or non normally distributed data, Wilcoxon rank-sum test may be performed to support the comparison.

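### The single ±5-day titer window in SAP 3.11 is narrower than the visit schedule at Days 85 and 181 and overlaps between Days 8 and 15, so on-schedule samples could be left out and, in limited cases, one sample can serve two visits

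*SAP*

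**What the plan says.** The Schedule of Events (Protocol Table 2, repeated as SAP Table 1-2) gives these tolerances for the antibody visits: Day 8 ±1, Day 15 ±2, Day 29 ±2, Day 85 ±7 and Day 181 ±7.

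SAP 3.11 opens with a general rule: "All data will be tabulated per the evaluation visit as recorded on the CRF even if the assessment is outside of the visit window". For the two titer endpoints it then gives a different one: "analysis visits will be derived based on the relative study day", "as outlined in the schedule of assessments with an expanded interval of +/-5 days". A tie-break follows. "If there is more than one immunogenicity assessment during a given interval for analysis", then "the immunogenicity assessment within the protocol-specified interval (+/- 2 days) will be used"; if several remain, the one closest to the target day is taken.

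SAP 2.1 points elsewhere: "Intervals for analysis, i.e., visit windows, are further defined in the Schedule of Events".

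Titers are analysed at every antibody visit. SAP 4.3.1 gives geometric means with "95% confidence limit will be provided on Days 1, 8 (if tested), 15, 29, 85, and 181". Fold increases, pairwise tests, ANOVA, seroconversion and seroresponse cover the same post-baseline days. On missing values, SAP 3.10 says: "In general, there will be no substitutions made to accommodate missing data points".

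**The concern.** One tolerance is applied to visits whose scheduled tolerances run from ±1 to ±7 days. That has three consequences.

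- **Days 85 and 181.** The analysis window is tighter than the visit window. A subject who attends when the protocol allows can have a valid titer that belongs to no analysis visit. Groups of 10 and 6 leave little room for such losses in the durability comparisons.
- **Days 8 and 15.** The windows overlap, and no rule says that a sample may serve only one visit. A titer from Day 13 could be reported as Day 8. Titers may be rising between these visits, and Protocol 1.3 says that time to seroconversion could matter for dose selection in outbreak use.
- **Tie-break.** It describes ±2 days as the protocol's interval for all visits, which the schedule does not support.

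The three statements about windows (the titer rule, the general CRF-visit rule and SAP 2.1) also lead to different data sets. Two programmers could both follow the SAP and produce different Day 85 and Day 181 tables.

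**Working it through.** **Inputs.** Visit tolerances: Schedule of Events. Analysis tolerance of ±5 and tie-break of ±2: SAP 3.11. Group sizes 10 and 6, geometric SD 3.3, and 6.4-fold at 80% power: SAP 3.1.

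**Step 1: the windows (target day ± tolerance).**

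| Visit | Schedule | SAP ±5 | On-schedule days outside ±5 | Is ±2 the scheduled tolerance? |
|---|---|---|---|---|
| Day 8 | 7-9 | 3-13 | none | no (±1) |
| Day 15 | 13-17 | 10-20 | none | yes |
| Day 29 | 27-31 | 24-34 | none | yes |
| Day 85 | 78-92 | 80-90 | 78, 79, 91, 92 (4 of 15) | no (±7) |
| Day 181 | 174-188 | 176-186 | 174, 175, 187, 188 (4 of 15) | no (±7) |

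The ±5 cannot be read as added to the scheduled tolerance, because the per-protocol definition in SAP 2.1 gives Day 29 as ±5 in total.

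**Step 2: overlaps.** Days 3-13 and 10-20 share Days 10, 11, 12 and 13. Of these, only Day 13 is on schedule for either visit (Visit 6). No other neighbouring windows touch (20 v 24, 34 v 80, 90 v 176).

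**Step 3: the tie-break applied to pairs of Visit 5 and Visit 6 days.**
- Both on schedule (Days 7-9 and 13-17): each sample goes to its own visit. With Days 9 and 13, both lie in the Day 8 window, but only Day 9 is within ±2 of Day 8. No double use.
- Visit 5 missed, Visit 6 on Day 13: there is one sample in each window, so the tie-break is not triggered and Day 13 fills both visits.
- Off-schedule pair, Days 5 and 10: both lie in the Day 8 window and Day 10 is within ±2, so it is chosen. Day 10 is also the only sample in the Day 15 window. Double use.
- Off-schedule pair, Days 5 and 13: both lie in the Day 8 window and neither is within ±2. The rule gives no answer.

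**Step 4: share of on-schedule samples lost at Day 85 or 181.** The documents give no visit-day distribution, so these are scenarios.
- Even spread over 15 days: 4/15 = 27%.
- Bell-shaped around the target, restricted to ±7 days. Weight at offset k is exp(−k²/2σ²), and the loss is the weight at |k| = 6 or 7 divided by the total weight. For σ = 3: 2 × (0.1353 + 0.0657) / 7.429 = 0.402/7.429 = 5.4%. In the same way, σ = 2 gives 0.5% and σ = 4 gives 11%.

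**Step 5: effect on the detectable fold.** Two-sided t-test at 0.05 on the log scale, SD = ln 3.3 = 1.194, noncentrality = ln(fold) / [1.194 × √(1/n₁ + 1/n₂)].
- Plan's own figure, 10 v 6: 6.4-fold gives 79.9% power, so the stated figure is reproduced.
- One subject lost per group, 9 v 5: 80% power needs 7.6-fold.

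The geometric SD of 3.3 is the plan's assumption for Day 29 ELISA, taken from another vaccine. Carrying it to Days 85 and 181 is a further assumption.

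**The case against.** The strongest reply is that the SAP never says that out-of-window titers are excluded. The general sentence in 3.11 keeps data under the recorded visit, SAP 2.1 would give ±7 days at the late visits, and CRF data stay in the listings. This stands in part. A reader might infer that on-schedule samples are certain to be dropped. The documents support only that they could be: exclusion is the natural reading of the titer-specific sentence, but it conflicts with two other statements.

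A reader might also infer that one sample will routinely fill two visits. Step 3 shows otherwise. It takes a missing or off-schedule sample, and Day 8 titers are reported only if tested.

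A third tempting inference is a large loss of power. Even spread and groups rounded down to 7 v 4 would need 10.6-fold. But 10 × 11/15 = 7.3 and 6 × 11/15 = 4.4, so the rounding adds to the figure (unrounded sizes give about 9.5-fold). SAP 3.11 also expects visits to follow the schedule, which makes clustering near the target more plausible than an even spread. SAP 3.1 adds that the sample size was not designed for formal hypothesis testing, although SAP 3.2 does plan formal tests of the secondary immunogenicity endpoints.

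Finally, the primary immunogenicity endpoints are on Days 1 and 29. At Day 29 the ±5 window is wider than the schedule and overlaps nothing, and per-protocol membership rests on Days 1 and 29 only. This stands in full.

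**Conclusion.** The concern holds for the secondary time points and should be fixed. Followed as written, the titer rule leaves 4 of the 15 permitted days at each of Days 85 and 181 without an analysis visit, and it contradicts both SAP 2.1 and the general rule in the same section. The Day 8 and Day 15 overlap is real but matters only when one of those samples is missing or off schedule. The ±2 in the tie-break is right for Days 15 and 29 only, and the tie-break is silent when no sample lies within ±2.

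The size cannot be fixed from the documents. Under the assumptions shown, between about 0.5% and 27% of on-schedule samples at each late visit are affected, with the top of that range needing an even spread of visits. In groups this small, one loss per group raises the detectable fold from 6.4 to 7.6, if the Day 29 geometric SD applies. The primary Day 29 analysis is not affected.

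**What to change.** In SAP 3.11:

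1. Replace the common ±5 days with visit-specific, non-overlapping windows no narrower than the Schedule of Events. One workable set is Day 8: 3-11; Day 15: 12-20; Day 29: 24-34; Day 85: 78-92; Day 181: 174-188. These leave no on-schedule day outside its window and put no day in two windows. The cut-points are an illustration; others meeting both conditions would do.
2. State that each sample may serve one analysis visit only.
3. In the tie-break, replace the ±2 days with the Schedule of Events window for that visit, then the sample closest to the target day.
4. Say that the titer rule takes precedence over the general CRF-visit sentence, and make SAP 2.1 refer to the windows in 3.11.

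Day 8 and Day 15 titers fall within the data available to the Day 29 interim analysis, so the change is best made before that freeze. It costs SAP wording only. The downside is that a few samples sit slightly further from the nominal day.

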3.12. Interim Analyses

One administrative Interim Analysis (IA) will be performed when all 36 subjects have completed the Day 29 follow-up, to guide dose selection for a subsequent clinical trial in one or more endemic countries in Africa. For this IA, the records to be included from each subject will be 'frozen' after being monitored and queries will be resolved without unblinding the site staff. Tables, listings, and figures will be provided by the treatment group to describe solicited local and systemic AEs, unsolicited AEs, and any MAAEs or SAEs, along with simple descriptive

statistics of clinical laboratory data. Neurologic findings through Day 29 will also be summarized.

For immunogenicity analyses, tables, listings, and figures will describe the serum IgG ELISA and PsVNA for each treatment group. In addition, RT-qPCR results from plasma, urine, and saliva samples will be used to assess viremia and shedding.

4. STUDY ANALYSES

4.1. Subject Disposition

Subject disposition will be tabulated and include the number screened, the number randomized, the number treated in total and by dose level, the number in each subject population for analysis (ASaT mITT, PP), the number who withdrew prior to completing the study (lost to follow up) and reason(s) for withdrawal, including withdrawal due to intolerance to the study injection.

A by-subject data listing of study completion information including the reason for premature study withdrawal, if applicable, will be presented.

4.2. Demographics and Baseline Characteristics

Demographics and baseline characteristics will be summarized and presented by treatment group. Age, height, weight and BMI will be summarized using descriptive statistics (number of subjects, mean, standard deviation, median, minimum, and maximum). The number and percentage of subjects in each gender, ethnicity and race category will also be presented.

Medical history will be tabulated and provided in data listings.

Demographic and baseline data such as for pregnancy test and screening results for HIV, HCV and HepB for each subject will be provided in data listings.

4.3. Immunogenicity Evaluation

Immunogenicity analyses will be conducted using the PP population. Supportive analyses of immunogenicity will be based on the mITT population if the number of subjects excluded from PP population is more than 10%.

4.3.1. Geometric Mean Titers and Mean Fold Increase of IgG ELISA Antibody and Neutralizing Antibody PsVNT

For IgG ELISA antibody titers and neutralizing antibody titers PsVNT (PsVNT₅₀ and PsVNT₈₀), GMT, and 95% confidence limit will be provided on Days 1, 8 (if tested), 15, 29, 85, and 181, where the GMT is calculated as the anti-log of the base-2 log transformed mean and the same for the corresponding confidence limit. Results will be presented by treatment group along with a combined PHV01 group, and the descriptive statistics will include the GMT, the geometric standard deviation, 25th percentile, median, 75th percentile, minimum, and maximum values. If appropriate, the analyses will be repeated for the GMT using the anti-log of the base-10 log transformed mean.

Pairwise comparison of the above antibody titer levels for each PHV01 dose level to one another and to the placebo group, as well as the comparison of the combined PHV01 dose group relative to the placebo group will be performed with Satterthwaite t-tests. T-tests will be performed on log-2 transformed values and the resulting estimated mean difference and associated 95% CI will then be back transformed using base-2 antilogarithms to obtain estimates

on the ratio scale. If appropriate, the analyses will be repeated using base-10 log transformed values and back transformed using base-10 antilogarithms to obtain estimates. In the event of extreme outliers or non normally distributed data, Wilcoxon rank-sum test may be performed to support the comparison.

Additionally, Analysis of Variance (ANOVA) models will be used to compare each PHV01 dose level to one another and to placebo for Days 8 (if tested), 15, 29, 85 and 181. The response variable will be the log-2 transformed ELISA titer values for the time point under consideration. If there is a significant difference between the GMTs, i.e., where the p-value from the F-test is < 0.05, then post-hoc pairwise tests using Tukey's method will be used to compare each dose with one another and each dose with placebo. The estimated mean differences on the log-2 scale between the treatment groups will be expressed as the ratio of GMTs. The base-2 antilogarithm of each mean difference represents the GMT ratio and the base-2 antilogarithms of the 95% CI limits for the mean difference represent the confidence limits for the GMT ratio.

Similarly, the mean fold increase of ELISA titers and PsVNT will be calculated by subtracting the base-2 log transformed values at baseline (Day 1) from the respective study day (Day 8 [if tested], 15, 29, 85, 181) for each subject and averaged within treatment group. If baseline titer value is <LLOQ or <LOD (ELISA only), baseline will be assigned as LLOQ/2 for purposes of deriving fold increase. The results will be presented by transforming back the anti-log. The 95% CI will be calculated based on the inverse of the log2 transformed fold increase values from the t-distribution. Results will be presented for each study day (Day 8 [if tested], 15, 29, 85, 181) by treatment group along with a combined PHV01 group, and the descriptive statistics will include the geometric mean fold-increase from baseline, the geometric standard deviation, 25th percentile, median, 75th percentile, minimum, and maximum values.

Pairwise ratios of the geometric mean fold rise and the associated 95% confidence intervals will be estimated for each PHV01 dose group relative to one another and to the placebo group, as well as the ratio of the combined PHV01 dose group relative to the placebo group on Days 8 (if tested), 15, 29, 85, and 181. Pairwise comparisons will be performed using Satterthwaite's t-test. T-tests will be performed on log-2 transformed values of the individual fold-rise values. The resulting estimated mean difference and associated 95% CI will then be back transformed using base-2 antilogarithms to obtain estimates on the ratio scale.

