3.3. MEASURES TAKEN TO MINIMIZE/AVOID BIAS

3.3.1. Randomization

This is a single-blind study, with group assignment hidden from site staff (apart from the compounding pharmacist) and subjects, along with a blinded CRA who will monitor the site records. To further avoid the potential for bias, the Medical Monitors (Sponsor and CRO) will remain blinded as well, until the database is frozen for the interim analysis (IA). Randomization will be stratified to achieve balance of sex across PHV01 dose levels and placebo recipients. For each randomization number, 2 replacement subject randomization numbers will be generated. The treatment assignment for replacement subjects will be the same as the subject who is being replaced.

Study personnel will obtain treatment identification (ID) numbers from the Interactive Web Response System (IWRS) as eligible subjects, who have successfully completed the screening process and are deemed eligible to participate by the PI (or another designated Investigator), are enrolled and proceed to vaccination.

Care will be taken to ensure that recruiting and screening processes are unbiased with regard to race and gender. To maintain randomization, alternates will be used, if necessary, in the order in which they were deemed eligible. Alternates are allowed to join the next cohort if they still meet entry criteria.

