7. STATISTICAL METHODS

An SAP, providing details about the specific planned analyses and statistical tests, will be prepared and approved by the Sponsor and its designees prior to study database lock and unblinding of the single-blind subject treatment assignments.

For safety and immunogenicity endpoints, tests will be performed comparing each dose level to the placebo group. Additional tests may be performed between dose levels to determine dose response. All statistical tests will be performed at the 2-sided 5% level of significance. No adjustments for multiple testing will be considered. No imputations will be made for missing immunogenicity data.

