7.5.2. Analysis Addressing the Immunologic Study Objective

Primary analysis of immunogenicity will be based on the PP analysis population; a secondary analysis of immunogenicity may be based on the mITT population. All immunogenicity analyses will be performed by vaccine treatment group. If a subject withdraws from the study, only the data collected to the point of withdrawal will be included. Immunogenicity will be described in terms of the number of responders and the magnitude of response over time.

For the continuous immunogenicity endpoints such as IgG ELISA antibody titers (on days 1, 15, 29, 85, and 181) and neutralizing antibody titers PsVNT (on days 1, 15, 29, 85, and 181). The 95% confidence limits will be obtained by first obtaining the 95% confidence limits for the mean of log₁₀ translated values and then exponentiating the confidence limits.

Mean fold increase in PHV01 IgG ELISA titers and PsVNT on days 8, 15, 29, 85, and 181 compared to baseline (day 1) will be provided. For each respective study day, \log_{10} translated values from baseline will be subtracted from the respective study day for each subject and averaged within vaccine treatment group and dose level. The result will be exponentiated to return to the original scale. The analysis of mean fold increase in PHV01 IgG ELISA titers and PsVNT over time will be performed using MMRM.

Distribution of PHV01 IgG ELISA titers and PsVNT on days 8, 15, 29, 85, and 181 will be displayed as reverse cumulative distribution curves. Median duration of vaccinemia determined by RT-qPCR will be provided. The duration will be presented graphically using the Kaplan-Meier method. Proportion of subjects with vaccinemia detected by RT-qPCR, by study day through days 1 (at 0 and 6 hours), 2, 4, 8, 15, and 29 and by vaccine treatment group, will be provided with 95% CIs.

Seroconversion rate determined on days 8, 15, 29, 85, and 181 and corresponding 95% CI will be provided. Logistic regression models may be performed for comparison between dose levels and placebo.

Additional immunogenicity dose response between dose groups and over time for continuous and categorical endpoints may be assessed using MMRM and logistic regression models, respectively. For continuous endpoints, log_{10} translated values will be entered in the model as the dependent variable(s). Regarding dose-response analyses more details will be provided in the SAP.

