3. GENERAL STATISTICAL METHODS

3.1. Sample Size Justification

The sample size for this Phase 1 study (N=36 subjects; total N=10 per vaccine dose level [30 vaccinees and 6 placebo]) was selected to provide initial data and obtain estimates of safety and immunogenicity parameters and their respective variabilities. Group size is based on prior experience with ERVEBO safety studies and assumptions from the responses seen in the preclinical studies. This Phase I study is therefore designed with the goal of providing further information for better planning of future in-human studies. As this is a FIH study of PHV01, the sample size was established to provide reasonable information for descriptive purposes and not specifically designed for formal hypothesis testing.

Safety: With a sample size of 10 subjects, an upper bound of 30.9% is established for the 2-sided 95% confidence interval (CI) for the incidence of an AE in the case that the event is not observed according to the two-sided 95% (Clopper-Pearson) exact CI. Alternatively, when pooled together all 30 vaccinees, an upper bound of 11.6% is provided. This established the sample sizes needed to ensure minimal AE rates could be detected with confidence.

Immunogenicity: Clinical data for the rVSV-ZEBOV-GP Ebola vaccine showed that a dose of 3×10^6 pfu/mL yielded a Day 29 GMT IgG ELISA titer of 1400 EU/mL and geometric standard deviation (SD) of 3.3. Assuming that the variability in responses to PHV01 is similar, the proposed group sizes afford 80% (alternate 90%) power to detect a 6.4-fold (alternate 8.6-fold) increase, comparing geometric mean ELISA titer using a two-sided test with alpha=0.05 for each vaccine group with the placebo group. Alternatively, performing the same comparison against placebo by pooling all three treatment groups with a total 30 vaccinated subjects, we would have 4.7-fold and an alternate 5.9-fold with 80% and 90% power, respectively.

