3.2. General Methods

All data listings that contain or imply an evaluation date will contain a relative study day (Rel Day). Pre-treatment and on-treatment study days are numbered relative to the day of the first dose of study medication which is designated as Day 1. The preceding day is Day -1, the day before that is Day -2, etc. Post-treatment study days are numbered relative to the first dose and are designated as Day 1, Day 2, etc. for table and listing display. Data for time interval analysis and graphing will be displayed as days since dosing where Hour 6 timepoint on Day 1 is converted to 0.25 days.

All outputs will be incorporated into Microsoft Word or Excel files, or Adobe Acrobat PDF files, sorted and labeled according to the International Conference on Harmonisation (ICH) recommendations, and formatted to the appropriate page size(s).

Tabulations will be produced for appropriate demographic, baseline, immunogenicity, and safety parameters. For categorical variables, summary tabulations of the number and percentage of subjects within each category (with a category for missing data) of the parameter will be presented. For continuous immunogenicity variables, the number of subjects, geometric mean, median, geometric standard deviation (SD), minimum, and maximum values will be presented.

Other continuous variables (e.g., BMI) will be summarized by the number of subjects, mean, median, SD, minimum, and maximum values. Summarizations will be tabulated by treatment group.

Formal statistical hypothesis testing will be performed on the primary and secondary immunogenicity endpoints with all tests conducted at the 2-sided, 0.05 level of significance. Summary statistics will be presented, as well as CIs on selected parameters, as described in the sections below.

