3.6. Adjustments for Covariates

Additional exploratory analyses adjusted for covariates may be performed on an ad-hoc basis.

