3.7. Multiple Comparisons/Multiplicity

No adjustments will be made for multiplicity. Study objectives will be evaluated through a combination of statistical and clinical assessments, which is not consistent with an approach to adjust for multiple comparisons.

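### The Day 29 immunogenicity comparisons leave out the sex stratum, name no ordered dose contrast, test ELISA dose pairs by two rival methods, and drop the protocol's repeated-measures model without recording it

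*SAP*

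**What the plan says.** **Randomisation.** Protocol 3.3.1: "Randomization will be stratified to achieve balance of sex across PHV01 dose levels and placebo recipients". SAP 1.2.2, which describes the randomisation, does not mention the stratum.

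**Covariates.** SAP 3.6 plans no adjustment: "Additional exploratory analyses adjusted for covariates may be performed on an ad-hoc basis". Sex appears elsewhere only as a splitting variable: SAP 3.8 analyses the immunologic endpoints separately in men and women, and SAP 4.3.2 repeats seroconversion by sex.

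**Comparisons.** SAP 4.3.1 tests each dose against each other dose and against placebo by Satterthwaite t-tests on log2 titer, without adjustment. For ELISA titers it adds that "Analysis of Variance (ANOVA) models will be used to compare each PHV01 dose level to one another and to placebo". If the F-test gives p < 0.05, Tukey's method is applied to the same pairs. Neutralising titers and fold rises have the t-tests only. Neither method is named primary. SAP 3.7 says: "No adjustments will be made for multiplicity".

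**Dose response.** Protocol 7.1 says immunogenicity endpoints will be evaluated for a dose-response relationship, counting placebo as dose 0. Protocol 7.5.2 adds: "Regarding dose-response analyses more details will be provided in the SAP". It also says, without qualification, that fold increase over time will be analysed by MMRM. The SAP has no trend test, slope, ordered contrast or MMRM, although MMRM is in its abbreviation list. SAP 1.1.1 says the SAP will outline differences from the protocol, but no section lists this one, and SAP 6 defers changes to the study report.

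**The concern.** The Day 29 interim analysis is meant to guide dose choice for the next trial (Protocol 7.2, SAP 3.12), so the dose-v-dose comparison of titers will be read closely. As written, the plan offers three unadjusted pairwise tests and, for ELISA, a second and stricter verdict on the same pairs. It has no rule for which one counts and no single summary of how titer changes with dose. If the two verdicts differ, the choice between them is made after the data are seen.

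The missing sex term is a separate and smaller matter. When randomisation is stratified on a factor that predicts the outcome, leaving that factor out of the model makes standard errors somewhat too large. Subgroup analyses do not repair this: with an even split, each holds about five subjects per dose.

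The missing MMRM is a plain mismatch between two governing documents.

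**Working it through.** **Inputs.** 10 subjects per dose and 6 placebo; geometric SD 3.3, so SD on the ln scale = ln 3.3 = 1.194 (SAP 3.1). Two-sided 5%: "Formal statistical hypothesis testing will be performed on the primary and secondary immunogenicity endpoints with all tests conducted at the 2-sided, 0.05 level of significance" (SAP 3.2; Protocol 7 agrees). Assumptions not in the documents: a 2-fold GMT rise per 10-fold dose step; the lowest dose 20-fold above placebo; placebo SD either equal to the vaccine groups or near zero (titers at a floor); a 50:50 sex split.

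**1. The plan's own figure.** SAP 3.1 states "80% (alternate 90%) power to detect a 6.4-fold (alternate 8.6-fold) increase, comparing geometric mean ELISA titer using a two-sided test with alpha=0.05". For 10 v 6:
- SE = 1.194 x sqrt(1/10 + 1/6) = 0.617
- ln 6.4 / 0.617 = 3.01
- noncentral t with 14 df gives 79.9% power

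Solving for the fold gives 6.41 (80%) and 8.59 (90%). The pooled 30 v 6 comparison gives 4.66 and 5.94 against the stated 4.7 and 5.9. All four figures reproduce with an unadjusted t-test, so the sizing assumes no sex term.

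**2. Linear contrast against the existing high-v-low t-test.** With three equal groups equally spaced on log10 dose, the contrast weights are -1, 0, +1, so the linear contrast is high minus low.
- Effect = 2 x ln 2 = 1.386
- SE = 1.194 x sqrt(2/10) = 0.534
- Noncentrality = 1.386 / 0.534 = 2.60
- Contrast, variance pooled over three doses (27 df): 71% power
- t-test on two groups (18 df): 69% power

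The gain is about 2 points and comes only from the extra degrees of freedom.

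**3. The two ELISA methods on the same pair.** For any one pair, Tukey with 4 groups and 32 df needs |t| above 3.83 / sqrt(2) = 2.71; the t-test needs about 2.10 at 18 df. Simulated results for doubling per step:

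| Placebo | t-test, high v low | F-gate + Tukey, high v low | Methods disagree |
|---|---|---|---|
| Equal SD | 69% | 47% | 22% |
| At a floor | 69% | 55% | 14% |

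In essentially every disagreement the t-test is significant and Tukey is not.

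**4. No dose effect (simulated).**
- F-gate opens: 99.7% of trials or more, because placebo is in the model
- At least one of the three dose-pair t-tests significant: 12%
- At least one dose pair significant after gate + Tukey: 2.8% (equal SD) to 4.9% (floor)
- One linear contrast: 5%

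**5. Sex term.** Hold the total SD at 1.194 and let r be the male/female GMT ratio. Residual variance = 1.194^2 - (ln r)^2 / 4.

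| Assumed r | Detectable fold, dose v placebo, 80% power (13 df) |
|---|---|
| 1 | 6.5 |
| 1.5 | 6.3 |
| 2 | 6.0 |
| 3 | 5.3 |

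For the linear contrast in step 2 (26 df), power is 71% at r = 1, 72% at r = 1.5, 75% at r = 2.1 and 80% at r = 2.9.

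**The case against.** Much of the opposing case stands.

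- **A reader might infer that the SAP cannot show whether titer rises with dose.** It can. SAP 4.3.1 already yields a 1x10^7 / 1x10^5 GMT ratio with a 95% CI, and the square root of that ratio is the fold-change per 10-fold dose. Setting the linear contrast against Tukey alone would suggest a loss of 16 to 24 points (71% v 55% or 47%). Against the SAP's own t-test the loss is about 2.
- **A reader might infer that the uninformative F-gate leaves dose-v-dose comparisons unprotected.** The gate does open almost always, but Tukey itself holds false dose differences to 3-5%. The 12% belongs to the unadjusted t-tests, and both documents openly decline multiplicity adjustment.
- **A reader might infer that sex is ignored.** Sex-specific analyses are planned; what is missing is the model term. A gain of 4 points or more needs a male/female GMT ratio above about 2, which nothing in the documents supports.
- **A reader might infer that the protocol promises a dose-response test, or that dose selection is the trial's primary purpose.** The evaluation is firm, but between-dose tests and dose-response models are worded as optional. The primary objectives are safety and antibody responses, and SAP 3.1 calls the sample size descriptive.

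The descriptive framing does not dispose of the point, because SAP 3.2 commits to formal 5% tests of the primary and secondary immunogenicity endpoints. The MMRM wording in the protocol is not optional.

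**Conclusion.** The point holds in a limited form. Four gaps are established from the text: no sex term in any immunogenicity comparison despite stratified randomisation; no ordered dose contrast; two unranked methods for the same ELISA pairs, one of which is a multiplicity adjustment that SAP 3.7 says will not be made; and a committed MMRM dropped without record.

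The sizes are modest. The two ELISA methods conflict on lowest v highest dose in about 14-22% of trials if GMT doubles per step. Three unadjusted dose pairs carry a 12% chance of a false difference, against 5% for one named contrast. The power gain from the contrast is about 2 points, and from sex nil to about 1 point unless the sexes differ about 2-fold or more. These figures assume log-normal titers, geometric SD 3.3 in the vaccine groups and the placebo scenarios stated above. The case for change is pre-specification and agreement between documents, not a large recovery of power.

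**What to change.** 1. **Day 29 dose response.** For log2 titer, fit dose group + sex and pre-specify one linear contrast on log10 dose across the three vaccine groups. Report fold-change per 10-fold dose with 95% CI. Estimate the residual variance from the vaccine groups so that floor-level placebo titers do not enter it.
2. **Placebo.** State that the protocol's 0-dose level is handled separately, through dose-v-placebo comparisons that allow unequal variances, as the Satterthwaite tests now do.
3. **Pairwise method.** Name one as primary for ELISA. Drop the F-gated Tukey step, or label it supportive and reconcile it with SAP 3.7.
4. **MMRM.** Restore the protocol's model for fold rise over time, with sex as a factor, or record its removal as a change from the protocol.
5. **Stratum.** State the sex stratum in SAP 1.2.2 and amend SAP 3.6 to match.

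Settle these before Day 29 titers are tabulated by group. Cost: SAP wording, programming and one degree of freedom. No change to sample size, visits or assays.
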